## Section 2.0 **Background information**

Vitamin D can be found in plants, fortified foods, or be synthesized in the epidermis using ultraviolet B rays. Even with the multiple sources of vitamin D available, an estimated 1 billion people world-wide have deficient or insufficient levels of Vitamin D. The prevalence is higher in urban environments where modern culture results in increased indoor activities and sunblock use as well as ethnic populations where darker skin pigmentation requires increased sunlight exposure to produce an equivalent amount of vitamin D as their lighter skin counterparts. Vitamin D is most known for its role in calcium homeostasis. As a patient becomes deficient in vitamin D their calcium stores are depleted and they develop osteomalacia. In addition to bone abnormalities, patients with low vitamin D levels may also develop an osteomalacic myopathy. Low vitamin D stores in these patients are associated with increased body sway, decreased muscular strength, changes in gait, difficulties in rising from a chair, inability to ascend stairs and diffuse muscle pain. Longitudinal studies have shown increased risk of falls with increasing amount of musculoskeletal pain intensity and locations. These symptoms of musculoskeletal pain are similar in nature to the muscle pain, or myopathic events, associated with statin use. In fact, patients with statin-induced myopathic events had lower serum vitamin D levels than statin-treated patients without myopathic events. Treatment with vitamin D in both statin-induced myalgic patients and the elderly has shown to reduce the occurrence of myopathic symptoms and falls, respectively. Unfortunately, the study by Ahmed et al was a non-randomized trial with subjective patient reporting as the measurable outcome. In addition, the lack of a control prevents assessment of whether these myalgic symptoms would have resolved independently with time. Both these factors may have led to a falsely elevated improvement in statin-induced myalgia; therefore, further randomized control trials are indicated to assess the validity of these findings.

Early in vitro studies have shown the presence of vitamin D receptors (VDR) on muscle cells. In fact VDRs on muscle cells have been shown to decrease with age; similarly, increasing age is a risk factor for developing statin-induced myalgias. Physiologically, vitamin D may directly bind to nuclear receptors in muscle tissue to improve muscle strength or directly increase intracellular phosphate concentrations resulting in increased ATP production and hence improved muscle functioning. An alternate theory involves competition of the cytochrome P-450 3A4 (CYP3A4) isozyme that is both responsible for statin metabolism and vitamin D activation. It is theorized that in vitamin D deficient states, CYP3A4 preferentially hydroxylates 25 OH D instead of metabolizing statins, leading to statin-induced toxicity. Statins that most commonly cause myopathic pain (simvastatin and atorvastatin) inhibit the CYP 3A4 system.

## **Section 3.0 Trial Purpose and Hypothesis**

### **Purpose:**

Statins are a highly effective therapeutic intervention for lipid optimization. Compliance is often limited by myopathic pain symptoms. The purpose of this study is to test if treatment with vitamin D can alleviate statin-induced myopathic pain in subjects with serum vitamin D levels  $\leq$  30ng/mL. This could provide patients a low cost, low risk intervention that would enhance statin compliance.

### **Hypothesis:**

We hypothesize that vitamin D therapy will improve statin-induced myopathic symptoms compared to placebo.

## **Section 4.0 Trial Design**

### *4.1 Participant Selection and Overall Trial Design*

Los Angeles based community physicians and the principal investigator's patients will be recruited for the study. This will serve to attract a primarily urban and ethnically diverse population of subjects. Only outpatients will be used for the study. We will enroll patients with an indication for statin therapy that are experiencing benign, mild to moderate myopathic symptoms such as: myalgia, myositis and myopathy but not rhabdomyolysis but are still able to continue their current statin medication. Rhabdomyolysis will be ruled out with a serum creatine kinase (CK) level  $< 10 \times$  the upper limit of normal (ULN). These definitions are based on the ACC/AHA/NHLBI guidelines as they are more clearly defined than FDA or NLA definitions for myopathic symptoms related to statin use (Appendix A). Clinician interview will determine that source of pain is myopathic and that myopathic pain is related to statin use. Other etiologies of myopathic pain will be ruled out such as; increased physical activity, hypothyroidism, trauma, falls, accidents, seizure, shaking chills, infections, carbon monoxide poisoning, polymyositis, dermatomyositis, alcohol abuse, and drug abuse (cocaine, amphetamines, heroin, or PCP). If serum vitamin 25 OH D levels are less than 30ng/mL, then the patient will be eligible for the study, as these patients are considered vitamin D deficient. The patient will continue their current statin regimen and will be randomized to either the placebo arm or treatment arm, which is the Vitamin D arm (Appendix B). All statin medications will be studied in this trial.

### *4.2 The primary aims of our study include:*

1. Assess if treatment of vitamin D deficiency improves statin-induced myopathic pain
2. Assess if treatment of vitamin D deficiency improves statin tolerance
3. Assess if treatment of vitamin D deficiency improves the quality of life in patients with statin-induced myopathic pain

### *4.3 The primary outcomes of our study include:*

1. Myopathic pain
2. Quality of life
3. Vitamin 25 OH D levels
4. Statin tolerability

These will be measured used the brief pain inventory (Appendix C), the SF 12 survey (Appendix D), serum measurements, and pill counting, respectively.

*4.4 The secondary outcomes* of our study include:

1. Parathyroid hormone (PTH)
2. Calcium
3. Lipid profile

PTH and calcium levels are directly dependent on serum 25 OH D levels. In addition, lipid profiles are affected by statin compliance.

*4.5 The modifiable variable* in our study is:

Number of medications patient is taking that is metabolized by the CYP3A4 enzyme

One of the proposed mechanisms of action in statin-induced myalgia and vitamin D deficiency involve competition at the CYP3A4 enzyme. Therefore, the total amount of CYP3A4 dependent medications each patient consumes will be tabulated to assess if it confounds outcomes at the end of the study. This will be most relevant for those patients who entered the study with a statin that is metabolized utilizing the CYP3A4 enzyme (lovastatin, simvastatin, atorvastatin, rosuvastatin, fluvastatin). Because 3 of these 5 statins are available in generic formulation, they will most likely be prescribed at a higher frequency in our urban dwelling population. This will be done with a medication list review (Appendix E).

*4.6 Study population*

Recruitment of patients will occur during outpatient clinic visits and through outpatient referrals from Los Angeles-based community physicians. Community physicians will not be sharing detailed study information with patients. Our study population will consist of 40 male and female urban dwelling patients of varied ethnic origin. Although women are preferentially affected by osteoporosis and the phenomenon under study may be similar to osteomalacic myopathy, we will include men in the study for inclusiveness. All women of child bearing age included in the study must be using an effective form of contraception because statin therapy can be harmful to a growing fetus. These women are all already on statin therapy so they cannot be pregnant as per clinical care. However, to ensure patient safety, all women will undergo urine pregnancy testing at the beginning of the study. Lactating women, however, can transmit statins to children through breast milk; therefore, they will be excluded from our study.

*4.7 Safety*

In order to assess if patients meet all inclusion and exclusion criteria, the patient will have to be interviewed, their chart reviewed, blood pressure measured, and have a urine pregnancy test (child bearing women). To ensure it is safe for the patient to begin the study, the chart will be reviewed to ensure baseline laboratory values within the last 6 months are within normal limits: creatinine (Cr), calcium (Ca), aspartate aminotransferase (AST), alanine aminotransferase (ALT), albumin (alb). Serum thyroid-stimulating hormone (TSH) values need to be within normal limits within the last 12 months. If these labs are not current, they will be re-drawn at the beginning of the study. Blood pressure will be measured prior to initiation of study since some research suggests that vitamin D therapy can lower blood pressure. Finally, the patient will have to be interviewed to assess if they meet all inclusion and exclusion criteria.

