## **Section 9.0.       Statistics**

Our goal sample size of enrolled patients is 40, with 20 patients in each arm. We approximate 10% of patients that we approach regarding the study will actually meet all inclusion and exclusion criteria as well as agree to the study; therefore, we estimate that we will have to approach approximately 400 patients.

**9.1 DataAnalysis for Baseline Comparability.** To establish comparability between the groups at baseline, all subjects randomized will be compared with respect to the baseline variables, including the primary and secondary outcome variables, demographics, reproductive history, risk factors, medical history, current medications, and physical exam variables. Comparisons between treatment groups will be performed using two sample t-test for normally-distributed continuous variables, Wilcoxon rank-sum test for non-normal or ordinal data, and Chi-square test for categorical variables. To evaluate whether a variable follows a normal distribution, we will use the Q-Q plot and Kolmogorov-Smirnov test.

**9.2. Data analysis to assess group difference at exit.** If there is no systematic group difference in the primary and secondary outcome variables at baseline, comparisons of these variables between the groups will be conducted using measurements taken at study exit. Two sample t-test will be used for normally-distributed variables, Wilcoxon rank-sum test for non-normal or ordinal data, and Chi-square test for categorical variables. For variables that show group differences at baseline, change scores will be used in the above analysis. Change scores will be calculated as the difference between study exit and baseline. Secondary analysis to assess group difference will be carried out using regression models to adjust for baseline covariates/factors that show group difference in 9.1. The outcomes in the regression analysis are the measurements at exit or change scores. We will use linear regression for continuous outcome variables (may be subject to transformation), logistic regression for binary variables, and proportional odds models for ordinal data.

**9.3 Study Power.** This is a pilot study, so a formal sample size calculation for statistical power is not included. Estimates of between-group difference and data variability will be used to conduct a more definitive sample size calculation for a larger study.

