## Appendix E CYP3A4 Medication List

CYP3A4 Medicine	Study Onset	Study Completion
Amiodarone		
Amlodipine		
Carbamazepine		
Clopidogrel		
Diltiazem		
Fluconazole		
Fluoxetine		
Esomeprazole		
Gemfibrozil		
Nifedipine		
Phenytoin		
Rifampin		
Verapamil		
Mibepradil (posicor)		
Ezetimibe		
Niacin		
Sildenafil		
Quinidine		
Clarithromycin		
Erythromycin		
Ketoconazole		
Itraconazole		
Terbinafine		
Protease Inhibitors		
Cyclosporine		
Nefazodone		
Midazolam		
Supplement w/Vitamin D and corresponding dose		
Total		

Appendix G: FLOWCHART OF PROCEDURES	Screen Visit	Initial Research Visit #1 Week 0	Visit #2 Phone Follow-up Week 1-2	Visit #3 (Week 8)
Standard of Care Procedures: Procedures that are part of regular care and would be done even if you did not take part in this research study				
Confirm myopathic pain from statin	X			
Medical record review, labs: ast/alt/alb/ca/cr/tsh, vital signs	X			
Chart review vitamin 25 OH D < 30ng/mL	X			
Research Related Procedures: Procedures, drugs, devices, evaluations or other services done only because of your participation in this research.				
Review Inclusion/Exclusion Criteria	X			
Consent		X		
Physical Exam: including vital signs, height, weight, abdominal and hip circumference		X		X
Safety Measurements Phlebotomy:  Creatine kinase (ck) Creatinine (cr) Calcium (Ca)  Urine Pregnancy (U-Bhcg)		X  X  X		X  X  X
Primary and Secondary Measurements w/Phlebotomy: intact PTH, Ca, vitamin 25 OH D, total cholesterol, LDL, HDL		X		X
Primary outcomes survey measurements: SF-12, Brief Pain Inventory		X		X
Modifiable Variables Measurements: Medication Review: CYP3A4 medications, Supplement review		X		X
Initiation of Medication: Ergocalciferol vs Placebo		X		

Phone Follow-up: discuss tolerability of medications and evidence of any adverse events			X	
---	--	--	---	--

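### Section 4.3 names four co-equal primary outcomes and Section 9.2 gives none priority, so the trial can report a positive primary outcome without any effect on pain

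*Combined protocol and SAP*

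**What the plan says.** The hypothesis in Section 3.0 is about one thing: that "vitamin D therapy will improve statin-induced myopathic symptoms compared to placebo". The purpose statement in the same section likewise speaks only of myopathic pain.

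Section 4.2 ("The primary aims of our study include") then lists three aims, unranked: pain, statin tolerance and quality of life. Section 4.3 ("The primary outcomes of our study include") lists four outcomes, also unranked: myopathic pain, quality of life, 25 OH D level and statin tolerability. The instruments follow in one sentence: "These will be measured used the brief pain inventory (Appendix C), the SF 12 survey (Appendix D), serum measurements, and pill counting, respectively". No questionnaire score is chosen and no summary of the pill count is defined. The procedure flowchart in Appendix G repeats the two questionnaires as primary, again without a score: "Primary outcomes survey measurements: SF-12, Brief Pain Inventory".

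Section 9.2 treats all primary and secondary outcomes alike. Where the groups do not differ at baseline, "comparisons of these variables between the groups will be conducted using measurements taken at study exit"; where they do, change scores replace exit values. The tests depend only on the type of data: "Two sample t-test will be used for normally-distributed variables, Wilcoxon rank-sum test for non-normal or ordinal data, and Chi-square test for categorical variables". The section gives no significance level, order of testing or multiplicity rule, and does not say which result carries the conclusion. Section 9.3 describes a pilot without a power calculation, whose estimates of group difference and variability will be used to size a larger study.

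**The concern.** The documents ask one question and allow four primary answers. Three of those answers are clinical, so if vitamin D has no clinical effect there are three chances, not one, of a nominally significant primary result. A null result on pain could then sit beside a significant result on quality of life or pill count, with nothing in the plan to say which of them answers the hypothesis.

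The fourth outcome, 25 OH D, is a different kind of problem. Patients are selected for a low level, and Section 6.0 describes ergocalciferol as the standard of care for treating deficiency. A difference between the arms on 25 OH D is therefore expected whatever happens to pain. It would be a true finding, but it would say nothing about the hypothesis. Yet under Section 4.3 it counts as a primary outcome met.

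Section 2.0 justifies this trial on the ground that an earlier uncontrolled study with subjective reporting may have overstated the benefit. Leaving the deciding outcome open weakens the protection that randomisation and blinding are meant to give.

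**Working it through.** **No figure to reproduce.** The plan states no alpha, familywise error rate or power, so the check starts from assumptions.

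**Inputs**
- 20 patients per arm (Sections 6.0 and 9.0).
- Three clinical primary outcomes: pain, quality of life, tolerability (Section 4.3). 25 OH D is left out of the false-positive count because a real difference is expected on it.
- Assumption: each test two-sided at 5%, hence 2.5% in the direction favouring vitamin D.
- Assumption: common correlation between outcomes of 0 to 0.7. The documents give no correlation.

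**Three independent tests**
- At least one false positive in either direction: 1 − 0.95³ = 1 − 0.8574 = 14.3%.
- At least one favouring vitamin D: 1 − 0.975³ = 1 − 0.9269 = 7.3%.

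**Correlated tests.** These come from a simulation of two-sample t-tests on normal outcomes, 20 per arm, 40,000 replicates. At correlation 0.5, three tests give about 12.5% in either direction and 6.2% favouring vitamin D.

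**If each questionnaire yields two scores.** The documents give no scoring, so this count is an assumption: two pain scores, two quality-of-life scores and the pill count make five tests.
- Independent, either direction: 1 − 0.95⁵ = 22.6%.
- Independent, favouring vitamin D: 1 − 0.975⁵ = 11.9%.

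| Clinical tests | Correlation | Any false positive | Favouring vitamin D |
|---|---|---|---|
| 1 | – | 5% | 2.5% |
| 3 | 0 | 14.3% | 7.3% |
| 3 | 0.5 | 12.5% | 6.2% |
| 5 (assumed) | 0 | 22.6% | 11.9% |
| 5 (assumed) | 0.5 | about 18% | about 9% |
| 5 (assumed) | 0.7 | about 15% | about 7.5% |

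**25 OH D.** With 20 per arm, a two-sided 5% t-test has 80% power for a difference of 0.91 SD (noncentral t). The documents give no expected rise. If the arms differ on 25 OH D by 0.91 SD or more, the chance of a significant primary outcome is at least 80% with no effect on pain at all.

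**One primary or an adjusted set.** A single named primary returns the error to 5% two-sided and keeps the detectable difference at 0.91 SD. Keeping all four outcomes primary with Bonferroni means 0.05/4 = 0.0125 per test and a detectable difference of 1.10 SD. Choosing one outcome is the cheaper route for a trial of 40.

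The switch between exit values and change scores and the adjusted regressions in Section 9.2 add further options that are not counted here.

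**The case against.** The strongest reply is that this is a pilot. Section 9.3 omits powering and the plan promises no error rate, so none is breached. Pain comes first in both Section 4.2 and Section 4.3 and is the subject of the hypothesis, so a fair reader knows what matters most. This stands in part: the point is not a breach of a stated rate, and formal alpha adjustment is not needed. But first place in a list is not a priority rule, Section 9.2 does not use it, and the protocol still sets out to test a hypothesis.

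A second reply is that the two-sided percentages overstate the harm, because about half of those false positives would favour placebo. That is right. For three tests the relevant figures are about 6% to 7%, against 2.5%.

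Three stronger readings are tempting and are not supported:
- **That the plan contains five tests and a 22.6% error rate.** The count depends on questionnaire scoring that the documents do not give. The Brief Pain Inventory form is not in the text available for this review, so any scoring on it could not be checked, and Appendix D shows only the SF-12 items. The documents themselves support three clinical outcomes, or four outcomes with 25 OH D.
- **That the outcome for the larger study will be picked on noise.** Section 9.3 says that estimates of difference and variability will inform a sample size. It says nothing about choosing an outcome by significance.
- **That selective reporting is intended.** The plan leaves room for it; nothing in the text plans it.

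**Conclusion.** The point holds and should be acted on. Four unranked primary outcomes, analysed identically, do not match a hypothesis about myopathic symptoms, and a positive primary claim is possible with no benefit on pain. 25 OH D is the easiest route to such a claim and needs no false positive.

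For the three clinical outcomes, the chance of a spurious result is roughly two and a half to three times that of a single test, whether counted in either direction or only in favour of vitamin D. If each questionnaire yields two scores, it rises to 15–23% in either direction, or about 7–12% favouring vitamin D. All of this rests on an assumed two-sided 5% per test and assumed correlations of 0 to 0.7. The absence of a deciding outcome rests on the documents alone.

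**What to change.** - **Section 4.3:** name one pain score from the Brief Pain Inventory at the exit visit as the single primary outcome. Pain severity is one example; the documents do not favour it over another pain score, so the investigators should choose, and do so before unblinding.
- **Section 4.3:** move quality of life, statin tolerability and any other Brief Pain Inventory score to secondary. Move 25 OH D to secondary too, described as a check that treatment raised the level. If it stays, the easiest route to a positive primary outcome remains open.
- **Section 9.2:** fix the analysis scale of the primary score in advance (exit value or change from baseline), so that the baseline comparison does not decide it.
- **Section 9.2:** state that the conclusion on the hypothesis rests on the named pain score alone, and report every other outcome as an estimate with a 95% confidence interval.

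This changes wording only. Appendix G already collects both questionnaires at Week 0 and Week 8, and no alpha adjustment, extra visits or extra patients are needed. The cost is that Aims 2 and 3 and 25 OH D lose the primary label.

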#### *4.8 Course of Experiment*

During the patients routinely scheduled clinical care visit or at time of referral, the patient will be screened for study eligibility. Patients on any statin will be included. Patient must have clinically documented vitamin D level <30ng/mL within 6 months of study entry during screen. It will be determined during the screen that patients' myalgia symptoms are due to statin therapy and that patient is able to continue their current statin medication. Once all the inclusion/exclusion criteria are met, the patient is recruited into the study and scheduled for their first research visit. At research visit #1, patients will be consented for the study, have lab work drawn for safety and laboratory outcome measurements (primary and secondary outcomes), complete study surveys (SF-12 and BPI), medical history, and medication review documents. They will also undergo a physical exam where blood pressure, height, weight, vital signs, abdominal and hip circumference measurements will be taken. The patient will then be randomized to either a treatment or placebo group and given the study drug. The study will be double-blinded. The treatment group will receive Ergocalciferol therapy at 50,000IU for 8 weeks while the placebo group will receive a placebo pill that is identical in nature. Patients will be asked to continue their current statin. Once serum creatinine, calcium, urine pregnancy (child bearing women) if indicated and creatine kinase levels return, likely within the same day, patient will be given a phone call and asked to start study drug or placebo for the next 8 weeks. Patients will then be called by study investigators and/or coordinator in 1-2 weeks for a phone follow-up where tolerability of study drug will be discussed as well as discussion and documentation of any adverse events (AEs). During this phone call an exit appointment will be scheduled after completion of 8 week course of study drug vs placebo. If patient is unable to tolerate protocol an earlier exit visit will be scheduled. During the exit visit patient will undergo a repeat physical exam, complete surveys and medication review, and phlebotomy that will measure the primary outcomes, secondary outcomes, modifiable variables, and safety measurements: creatinine, calcium, and creatine kinase levels. For a temporal summary, please refer to Appendix G.

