### ***5.3 Withdrawal Criteria***

Patients who are severely intolerant to their current statin therapy, meaning hydration and rest do not improve symptoms, will be asked to exit the protocol. Patients will be brought back for their exit visits outlined in Appendix G and data regarding all measurable outcomes will be taken. In addition, remainder study drug will be collected. Patient will then be referred to primary care physician for further management of vitamin D deficiency, if persistent. In regards to statin management, patients will be withdrawn from their current statin and asked to follow up with their cardiologist or primary care physician for further statin therapy management.

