## **Section 8.0        Assessment of Safety**

When the vitamin D system is overstimulated, hypercalcemia results because of increased intestinal calcium absorption and by the induction of bone re-absorption. In regards to vitamin D, hypercalcemia is the criterion for harm, because it is the agent that causes symptoms. These symptoms include nausea, dehydration, lethargy, weakness, excessive thirst, anorexia, headache, constipation, weight loss, kidney stones, arterial calcium deposits and decreased or altered urine output. However, toxicity is a rare concern with vitamin D, especially since UVB rays degrade excess vitamin D. Serum 25 OH vitamin D levels are measured approximately 2 months after initiation of high dose ergocalciferol therapy to monitor efficacy as well as toxicity. This time period is consistent with the termination of our study, where we will obtain serum calcium and 25 OH-D levels to monitor efficacy and toxicity. Furthermore, the first signs of toxicity typically do not occur until a serum 25 OH D concentration of 100-140 ng/mL (>250nmol/L), which is unlikely to be obtained at high doses prior to the 3 month monitoring period that is currently the standard of care.

Statins, although rare, can cause rhabdomyolysis. This is the main concern when patients develop myopathic pain. If serum CK levels are > 10 x ULN then the patient is toxic from statin therapy, and further therapy with statins should be discontinued. Prior to study initiation, serum CK levels will be checked to screen out patients with rhabdomyolysis in whom continuation of statins is unsafe.

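### Adverse-event enquiry is scheduled only at the Week 1-2 phone call; the exit visit lists none, so other symptomatic or transient events after the call are not systematically recorded

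*Combined protocol and SAP*

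**What the plan says.** Section 4.8 puts the only named adverse-event activity, "discussion and documentation of any adverse events (AEs", at the phone follow-up 1 to 2 weeks after study drug is started. The matching row in Appendix G reads "Phone Follow-up: discuss tolerability of medications and evidence of any adverse events" and is marked under Visit #2 only.

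For the exit visit, Section 4.8 gives a list: "During the exit visit patient will undergo a repeat physical exam, complete surveys and medication review, and phlebotomy". The phlebotomy covers the primary and secondary outcomes and "safety measurements: creatinine, calcium, and creatine kinase levels". The Visit #3 entries in Appendix G correspond: physical exam with vital signs and weight, safety and outcome blood tests, the two surveys, and the medication and supplement review.

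On leaving early, Section 4.8 says "If patient is unable to tolerate protocol an earlier exit visit will be scheduled", and Section 5.3 says of withdrawn patients: "Patients will be brought back for their exit visits outlined in Appendix G and data regarding all measurable outcomes will be taken". Neither adds an adverse-event enquiry.

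Section 8.0 states that "hypercalcemia is the criterion for harm, because it is the agent that causes symptoms", names the symptoms it can cause, and relies on the end of the study, "where we will obtain serum calcium and 25 OH-D levels to monitor efficacy and toxicity". It schedules no symptom enquiry.

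**The concern.** The one scheduled enquiry comes early, when cumulative exposure to study drug is low. Section 8.0 puts the usual check for toxicity at about 2 months, which is when this study ends, yet the exit visit is not scheduled to ask about symptoms.

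If the schedule is followed as written, a symptom that begins after the call, does not lead to an early exit and leaves no trace in the exit measurements is recorded only if the patient mentions it. Spontaneous reporting can differ from patient to patient and between staff. The by-arm adverse-event comparison for the later part of treatment would therefore be less complete than for the first 1 to 2 weeks, and harder to interpret. Section 9 describes comparisons of baseline variables and of primary and secondary outcomes, and mentions no adverse-event summary.

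**Working it through.** The plan gives no figure for the interval after the last enquiry, so there is none to reproduce.

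**Inputs (Section 4.8; Appendix G).** Treatment lasts 8 weeks (56 days). The call is at week 1 to 2 (day 7 to 14). Exit is at Week 8, or earlier if the protocol is not tolerated.

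**Time from last scheduled enquiry to exit = exit week − call week.**

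| Exit | Call at week 1 | Call at week 2 |
|---|---|---|
| Week 8 (completer) | 8 − 1 = 7 weeks (56 − 7 = 49 days) | 8 − 2 = 6 weeks (56 − 14 = 42 days) |
| Week 4 (assumed, for illustration) | 4 − 1 = 3 weeks | 4 − 2 = 2 weeks |
| Arranged at the call and attended at once | about 0 | about 0 |

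These figures count the call from the start of study drug. If it is counted from Visit #1 and the start is delayed while laboratory results return (assumed 1 to 3 days), the completer interval grows by the same number of days: 43 to 50 days for 1 day, 45 to 52 days for 3 days. The 6 to 7 weeks is therefore not overstated.

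**What the exit visit captures, set against the symptoms in Section 8.0.**

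- Hypercalcemia itself: exit calcium, in both arms, at one time point.
- Lethargy and weakness: partly, through the SF-12 energy and function items.
- Weight loss: weight is measured at Visit #1 and Visit #3.
- Pain: Brief Pain Inventory, and the SF-12 pain-interference item.
- Nausea, excessive thirst, anorexia, headache, constipation, altered urine output: no scheduled item asks about these.

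**Reach of the SF-12.** Items 4 to 12 (9 of 12) ask about the previous 4 weeks. For an exit at Week 8 the recall starts at 8 − 4 = Week 4. Between the call and Week 4 there remain 4 − 2 = 2 to 4 − 1 = 3 weeks that those items do not reach.

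**Other candidates.** Appendix E records medications. Pill counting, the Section 4.3 measure of statin tolerability, records no symptom. Early exits can be counted by arm, and intolerance raised at the call is documented there.

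**The case against.** The strongest case against has four parts.

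*Absence from these lists is weak evidence.* Pill counting measures a primary outcome, yet it is not itemised at exit in Section 4.8 and has no row in Appendix G. Collection of remaining drug (Section 5.3) has no row either. The blank Week 8 cell in the phone row shows nothing, because that row describes the phone visit. This lowers confidence. It does not remove the point: adverse-event documentation was written explicitly at the call and is missing from the exit list a few sentences later, and neither Section 5.3 nor Section 8.0 supplies it.

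*The rule may be elsewhere.* Sections 7.0 and 10.0 and Appendices C and F are not in the supplied text (Section 4.3 identifies Appendix C as the Brief Pain Inventory), and the opening pages were removed. A reader might infer that the plan has no adverse-event procedure after Week 2; the documents as supplied cannot show that.

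*Much is measured at exit.* This stands. A reader might turn the interval into a share, (8 − 2)/8 = 75% to (8 − 1)/8 = 87.5% of treatment, and call that share unmonitored. It is only time elapsed since the call. The surveys, weight, vital signs, examination and blood tests give partial capture in both arms, and exit calcium addresses what Section 8.0 calls the criterion for harm. The share also says nothing about how many events would be missed.

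*The pilot's purpose is not harmed.* A reader might infer that Section 9.3 is undermined. That section seeks between-group differences and variability for a later sample-size calculation and assigns the pilot no task of estimating adverse-event rates, so the point does not rest on it. Nor is any primary comparison affected.

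**Conclusion.** The point holds in a narrow form. In the supplied text, adverse-event enquiry and documentation are scheduled only at the Week 1-2 call. For completers, 6 to 7 weeks pass between that enquiry and exit; for early exits the interval is shorter, down to about zero.

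Pain, energy, function and hypercalcemia at exit are covered in both arms. Other symptomatic or transient events after the call are not systematically recorded, so their by-arm comparison would rest largely on spontaneous reports and early exits. The documents do not allow an estimate of how many events this involves.

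The conclusion assumes that the unsupplied sections hold no such rule and that staff follow the schedule as written. Confidence is medium. The change is worth making because it alters what is collected at very little cost; it is not a reason to doubt the efficacy comparisons.

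**What to change.** Add a separate row to Appendix G for an adverse-event review, marked at Visit #3 and at any early exit visit and covering the time since Week 0. Do not reuse the phone-visit row. Add one matching sentence in Section 4.8 and one in Section 5.3, and have the question asked the same way in both arms. In the analysis, tabulate events by arm over the full treatment period, alongside the exit calcium, creatinine and creatine kinase results.

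If an unsupplied section or appendix already requires this, a cross-reference from Section 4.8 and Appendix G is enough.

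The cost is a few minutes at a visit already planned and one extra table. No visit or blood draw is added.
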